12.2 Withdrawal of Subjects from the Study

A subject may be withdrawn from the study at any time if the subject, the investigator, or the Sponsor feels that it is not in the subject's best interest to continue.

All subjects are free to withdraw from participation at any time, for any reason, specified or unspecified, and without prejudice.

Reasonable attempts will be made by the investigator to provide a reason for subject withdrawals. The reason for the subject's withdrawal from the study will be specified in the subject's source documents. As noted above, subjects who discontinue study treatment early (i.e., they withdraw prior to Visit 12) should have an early discontinuation visit. Refer to Section 10.13 for early termination procedures. Subjects who withdraw after Visit 1 but prior to Visit 10 should be encouraged to come in for a final visit (and the procedures to be followed would include those for their next scheduled visit). Subjects who sign the informed consent form (ICF) and who are discontinued or withdraw from the study before study product administration will be defined as screen failures. No data will be collected in the CRFs for screen failure subjects.

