2.2 Risk / Benefit Assessment

Details of the risk and benefits of dupilumab are outlined in the Prescribing Information. The most common adverse effects (incidence $\geq 1\%$) of dupilumab include injection site reactions, conjunctivitis, blepharitis, oral herpes, keratitis, eye pruritus, other herpes simplex infection, and dry eye. Other adverse effects include hypersensitivity reactions, including generalized urticarial and serum sickness or serum sickness-like reactions.

The risk to subjects in this trial will be minimized by compliance with the inclusion/exclusion criteria, proper study design, and close clinical monitoring.

In regards to skin biopsy procedures, as in any surgical procedure, there are certain inherent risks including bleeding, post-operative pain, infection, reactions to sutures, anesthetics or topical antibiotics, and scarring. All reasonable efforts will be made to minimize the possibility of these potential complications.

In regard to patch testing, in rare cases there may be blistering reactions, in highly allergic patients. It is possible in these instances for scarring to occur at the site of the offending allergen. Sometimes, particularly in patients with photodamaged skin temporary bruising can occur with removal of the tape from the patches. Patch testing, in rare circumstances, can lead to excited skin syndrome (typically in patients who have significant active dermatitis at the time of testing). To mitigate this, patients deemed to have no clear areas for testing due to significant active dermatitis will not be patch tested. Patients who are pregnant will also be excluded, as patch testing has not been studied in this population. We believe there is only minimal risk to those participating in any and all parts of this study. We also believe that the minimal risk is reasonable for the benefits gained by a better understanding of how dupilumab affects contact allergy. Additionally, patients will receive patch testing and allergen avoidance which is of immense benefit to improving their skin disease and quality of life going forward.

The benefit to subjects is that they will be receiving an approved therapy for moderate-to-severe atopic dermatitis. Although it cannot be guaranteed, dupilumab has shown to be safe and effective in moderate-to-severe atopic dermatitis. An additional benefit to patients is that they are contributing to society by helping the enhancement of science.

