8.4 Administration Instructions

All doses of study treatment will be administered at the study site after the study assessments for the visit have been completed at visits occurring between week 0 and 4, as well as weeks 8, 12, 16, 24, 36, and 44. After week 4 subjects will administer the medication independently every other week (weeks 6, 10, 14, 18, 20 22, 26, 28, 30, 32, 34, 38, 40, 42, 46, 48, and 50) only after they have shown the competency to self-administer the treatment outside of the study site. The medication will be administered via subcutaneous injection into the thigh or abdomen, except for the 2 inches (5 cm) around the navel. The upper arm can also be used if a caregiver administers the injection. There will be no medication given after week 50.

The subject should be instructed to contact the investigator if he/she is unable for any reason to attend a study visit as scheduled. All dates and times of injections done to the subject during the study must be recorded on the Dosage Administration Record CRF. The investigator will promote compliance by instructing the subject to attend the study visits as scheduled and by stating that compliance is necessary for the subject's safety and the validity of the study.

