10.2 Visit 1: PRE-TREATMENT PATCH TESTING

1. Application of contact allergens (20 minutes).
2. 48 hours later: removal of allergens and photography (30 minutes).
3. 120 hours later: final reading of allergens (10 minutes) and allergen avoidance counseling (approximately 30 minutes).

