11.2 Serious Adverse Experiences (SAE)

A SAE is any untoward medical occurrence that at any dose:

- results in death,
- is life-threatening,
- requires inpatient hospitalization or prolongation of existing hospitalization,
- results in persistent or significant disability/incapacity,
- is a congenital anomaly/birth defect,
- is otherwise a significant medical event.

This includes any SAEs likely to arise from the trial indication or progression of underlying/concomitant illness(es) (e.g. progression of cancer in oncology trials), unless specified in the protocol as study specific exemptions.

Any SAE, irrespective of causality, occurring after the subject has provided informed consent and until four weeks after the subject has stopped study participation must be reported unless otherwise stated in the protocol. SAEs occurring after four weeks from ending study participation should only be reported if considered by the Investigator attributable to the exposure to the investigational drug(s) during the trial period. This includes the period in which the study protocol interferes with the standard medical treatment given to a subject, even if study treatment has not yet started (e.g. withdrawal of previous treatment during washout period, change in treatment to a fixed dose of concomitant medication).

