11.3 Serious Adverse Experience Reporting

Study sites will document all SAEs that occur (whether or not related to study drug) per [UCSF IRB Guidelines](#). The collection period for all SAEs will begin after informed consent is obtained and end after procedures for the final study visit have been completed.

SAEs occurring after four weeks from ending study participation should only be reported if considered by the Investigator attributable to the exposure to the investigational drug(s) during the trial period. This includes the period in which the study protocol interferes with the standard medical treatment given to a subject, even if study treatment has not yet started (e.g. withdrawal of previous treatment during washout period, change in treatment to a fixed dose of concomitant medication).

In accordance with the standard operating procedures and policies of the local Institutional Review Board (IRB)/Independent Ethics Committee (IEC), the site investigator will report SAEs to the IRB/IEC.

Timelines: All serious adverse events (SAEs) must be reported by the sites to Sponsor within 24 hours of occurrence of the SAE. The timelines for investigator initiated trials reporting to Regeneron Pharmaceuticals and Sanofi-Genzyme will be done as per Third Party Study/Investigator Initiated Trial Agreement.

Follow-up reports: SAEs will be followed until resolution or until it is judged to be permanent, and an assessment will be made at each visit (or more frequently, if necessary) of any changes in severity, the suspected relationship to the drug of interest, the interventions required to treat it, and the outcome.

The Sponsor shall support Regeneron and Sanofi-Genzyme in the following-up of all SAEs so that complete information is available to maintain patient safety and also as part of any commitments by Regeneron and Sanofi-Genzyme to any Health authority OR specific Health authority follow-up requests for the product under investigation.

Pregnancies: Any occurrences of a pregnancy in a patient (or a patient's partner) during study participation will be collected. All pregnancies will be followed up to determine outcome, including spontaneous or voluntary termination, details of the birth, and the presence or absence of any birth defects, congenital abnormalities, or maternal and/or newborn complications.

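### Section 12.2 bars CRF data on anyone who leaves before the first dose, so harms of pre-dose procedures (mainly patch testing) in those subjects stay out of the CRF, database and safety tables, contrary to Sections 9.1.6 and 11.1

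*Combined protocol and SAP*

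**What the plan says.** Section 12.2 defines the group by timing alone. Subjects who have signed consent and are "discontinued or withdraw from the study before study product administration will be defined as screen failures". The next sentence reads: "No data will be collected in the CRFs for screen failure subjects". It makes no exception for adverse events, serious or not.

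Elsewhere the protocol says:

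- **Sections 10.1 to 10.3:** consent is at Visit 0, patch testing at Visit 1 and week 0 at Visit 2.
- **Section 9.2.5:** four 5 mm punch biopsies are taken at week 0.
- **Section 8.4:** "All doses of study treatment will be administered at the study site after the study assessments for the visit have been completed".
- **Section 9.1.6:** adverse events are captured for the duration of the study and entered on the CRF.
- **Section 11.1:** all adverse events go into the study database.
- **Section 11.2:** the SAE rule covers "Any SAE, irrespective of causality, occurring after the subject has provided informed consent" and includes time before study treatment starts, such as washout.
- **Section 11.3:** "The collection period for all SAEs will begin after informed consent is obtained".
- **Section 14.3:** safety is summarised for the 15 treated subjects.

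**The concern.** A no-data rule for screen failures is harmless when screening means a history, an examination and a blood draw. Here the same label covers people who have had study procedures with recognised harms. Section 2.2 says of patch testing that "in rare cases there may be blistering reactions, in highly allergic patients". It also names scarring and excited skin syndrome for patch testing, and bleeding, infection and scarring for biopsy.

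A subject who reacts to the allergens and decides not to continue becomes a screen failure, so the CRF stays empty. Two things are at stake. The site is given instructions that it cannot all follow. And the trial's own account of what its procedures did to consenting participants would omit those who had the procedures and never reached the drug.

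**Working it through.** No design figure (alpha, power, effect size, SD) enters this point. The check is one of sequence and of cross-reading.

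**1. What happens between consent and first dose**

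| Step | Source | Before first dose? |
|---|---|---|
| Consent, screening laboratory tests | 10.1 (Visit 0) | Yes |
| Patch-test application, removal at 48 h, final reading at 120 h | 10.2 (Visit 1) | Yes |
| Biopsies: 3 lesional + 1 non-lesional = 4 | 9.2.5; item 8 of 10.3 | Yes, same visit |
| Study medication | Item 10 of 10.3; 8.4 | First dose |

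Patch testing alone takes 120 / 24 = 5 days from application to final reading, and a subject can leave at any time in that period or before Visit 2. For biopsy the window is only the gap between items 8 and 10 of one visit. Four of the 4 × 4 = 16 planned biopsies precede the dose (25%), but that counts procedures, not records at risk. Patch testing is therefore the main exposure.

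**2. Recording rules for a subject who leaves in that window**

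- 9.1.6: adverse events are entered on the CRF. 12.2: no CRF data. These contradict each other.
- 11.1: all adverse events go into the database. 12.2: nothing is entered on the CRF that feeds it. These also contradict each other.
- 11.2 and 11.3: SAEs count from consent, but the duty is to report and document them, and neither section mentions the CRF. A site could satisfy these sections and 12.2 together. Section 11.2 also allows exceptions stated elsewhere in the protocol, so 12.2 could be read as one. This is an ambiguity, not a direct contradiction.
- 12.2 itself: subjects who withdraw after Visit 1 are encouraged to attend a final visit with the procedures of their next scheduled visit. Straight after patch testing that is Visit 2, whose first item is recording adverse experiences. For an undosed subject the result could not be entered.

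**3. Whether another part of the plan closes the gap**

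- The AE row of Appendix 1 has its first mark at week 0, and Section 10.2 lists no AE item at Visit 1. A subject who leaves after patch testing may never reach the first scheduled AE question.
- The AE definition in 11.1 refers to subjects who have been given a product. Read strictly, a patch-test reaction in an undosed subject is not an AE at all. That would soften the contradiction in step 2, but only by placing the harm outside the definition. It also fits poorly with Section 10.3, which records adverse experiences at week 0 before the first dose.
- Section 14.3 tabulates treated subjects only.

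**4. Records that remain outside the CRF**

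- Section 11.3: SAEs are reported to the Sponsor within 24 hours and to the IRB/IEC, and followed up.
- Section 16.5: the investigator reports AEs to the Sponsor and unanticipated problems to the IRB.
- Sections 15.1 and 12.2: source documents hold the observations and the reason for withdrawal.
- Sections 9.2.6 and 10.2: patch sites are graded and photographed.

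The harm would usually be on record somewhere, but not in the data set from which safety is tabulated.

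**The case against.** The strongest reply is that the absence of a CRF entry is not the absence of a record. The routes in step 4 are real, and serious events reach the Sponsor and IRB whatever 12.2 says. A reader might infer that pre-dose harms are lost altogether; the documents do not support that. This part of the objection stands.

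Second, safety evaluation in Section 5.3 concerns tolerability of dupilumab, and events in people never dosed cannot bias a summary of treated subjects. This also stands, and is why that summary should keep its population. It does not answer the contradiction with 9.1.6 and 11.1, which are not limited to drug effects in the tables.

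Third, the biopsy part is thin. Someone would have to leave between biopsy and injection at one visit, and complications that appear later would usually arise once the subject has been dosed. This stands; biopsy is a minor part of the point.

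Four further inferences are tempting and should not be drawn:

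- **That a given number of exposed people would go unrecorded.** The documents give no pre-dose attrition rate, and any such count would include leavers for every reason, not people harmed. Section 2.2 calls blistering rare.
- **That leavers are selected on harm.** This is plausible, but nothing in the documents shows it.
- **That the minimal-risk statement in Section 2.2 would be biased.** It is a prospective belief, not a conclusion from this trial's tables.
- **That the contact-allergy comparison suffers.** That aim is a before-and-after comparison under dupilumab, so a never-dosed subject has no second round to contribute.

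**Conclusion.** The point holds as an internal contradiction with a limited consequence. Section 12.2 cannot be followed together with 9.1.6 and 11.1 for a subject who has an adverse event during patch testing, or between biopsy and injection, and leaves undosed. It leaves the handling of SAEs under 11.2 and 11.3 ambiguous. The events would be absent from the CRF, the database and the safety tables, though not from every record.

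The number affected cannot be worked out from the documents. No primary or secondary endpoint, sample size or dupilumab safety result changes. The correction is worth making because it is cheap and because the plan itself names harms for these procedures. The conclusion assumes that Visit 1 is carried out before week 0 as scheduled, and that 12.2 means what it says.

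One possible origin, offered only as an inference: Section 8.6 still calls week 0 visit 1, so 12.2 may have been written before the patch-test visit was inserted.

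**What to change.** 1. **Section 12.2.** Either limit the no-CRF rule to subjects who had no study procedure beyond screening, or keep the rule and exempt a minimum set: consent date, procedures performed, reason for leaving, and all AEs and SAEs from consent. State that 12.2 is not an exception to the SAE rule in 11.2.
2. **Section 10.2 and Appendix 1.** Add an AE entry at Visit 1. The second patch-test visit involves subjects already dosed and is not part of this point.
3. **Section 11.1.** Extend the AE wording to events associated with study procedures from consent onward, so that 9.1.6, 11.1, 11.2 and 11.3 share one starting point.
4. **Section 14.3.** Add a separate listing of pre-dose procedural events for all subjects who underwent a study procedure. Leave the dupilumab safety summary on treated subjects.

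The cost is protocol wording, one short CRF page for undosed leavers and one listing. No visit or procedure is added.

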13 PROTOCOL VIOLATIONS

A protocol violation occurs when the subject, investigator, or Sponsor fails to adhere to significant protocol requirements affecting the inclusion, exclusion, subject safety and primary endpoint criteria. Protocol violations for this study include, but are not limited to, the following:

- Failure to meet inclusion/exclusion criteria.
- Use of a prohibited concomitant medication.
- Non-compliance with study drug regimen.
- Non-compliance with study visit procedures.
- Failure to comply with Good Clinical Practice (GCP) guidelines will also result in a protocol violation. The PI will determine if a protocol violation will result in withdrawal of a subject.

When a protocol violation occurs, it will be discussed with the investigator and a Protocol Violation Form detailing the violation will be generated. This form will be signed by a Sponsor representative and the Investigator. A copy of the form will be filed in the site's regulatory binder and in the Sponsor's files.

14 STATISTICAL METHODS AND CONSIDERATIONS

Prior to the analysis of the final study data, a detailed Statistical Analysis Plan (SAP) will be written describing all analyses that will be performed. The SAP will contain any modifications to the analysis plan described below.

14.1 Analysis of Primary Endpoint

CyTOF: One sample paired t-test comparing percentage change in lesional and non-lesional IL-4 positive, CD4+ T effector cells at weeks 2, 4, 12 compared to baseline.

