	
12. Treatment with oral antibiotics within 2 weeks of the baseline visit.
 
13. Treatment with any cell-depleting agents including but not limited to rituximab: within 6 months before the baseline visit, or until lymphocyte count returns to normal, whichever is longer, or use of other biologics: within 5 half-lives (if known) or 16 weeks prior to baseline visit, whichever is longer.
 
14. Physical or laboratory exam not within clinically acceptable limits.
 
15. Subjects possess other diagnoses that, in the investigator's opinion, preclude him/her from safely participating in this study or interfere with the evaluation of the subject's atopic dermatitis.
 
16. At baseline visit, the subject does not have sufficient clear skin for which to perform patch testing as determined by the investigator's opinion, which is also defined as approximately 50-75% of skin on the back clear of atopic dermatitis.
 
17. History of known or suspected intolerance to any of the ingredients of the investigational study product.
 
18. Pregnant or nursing (lactating) women, where pregnancy is defined as the state of a female after conception and until the termination of gestation, confirmed by a positive hCG laboratory test (>10 mIU/mL).
 
19. Women of child-bearing potential, defined as all women physiologically capable of becoming pregnant, unwilling to use effective contraception during the study and for 6 weeks after stopping treatment.
 
For healthy control subjects:
 
 1. No areas of non-inflamed skin. 2. History of autoimmune disease. 3. Subject is younger than 18 years of age.
STUDY TREATMENT	Dupilumab (Dupixent ®) 600 mg SC at week 0, then 300 mg SC every other week.
STUDY DURATION	The total duration of the study is expected to be 104 weeks: 52 weeks for recruitment and 52 weeks for site visits.
PRIMARY ENDPOINT	Percentage change from pre-treatment baseline of CD4+ T effector cells in lesional and non-lesional skin expressing IL4 at weeks 2, 4, 12 in dupilumab-treated patients.
SECONDARY ENDPOINT	Differentially expressed genes and pathways in each cell population at weeks 2, 4, 12 compared to pre-treatment baseline using RNA-seq.
SAFETY EVALUATIONS	Safety and tolerability will be assessed by adverse events, vital signs, physical examinations (including skin examinations and injection-site evaluations), and concomitant medication review. Laboratory assessments

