	will be performed at screening.
STATISTICS Primary Analysis Plan	CyTOF : One sample paired t test comparing mean change in lesional and non-lesional IL-4 positive, CD4+ T effector cells compared to baseline. RNA-seq : Identification of differentially expressed genes compared to baseline within each immune population studied using the statistical program Cuffdiff (paired analysis).
ETHICAL CONSIDER- ATIONS	This study will be conducted in accordance with applicable laws and regulations and according to the recommendations of International Conference on Harmonization Good Clinical Practice (ICH GCP) guidelines and those of the Declaration of Helsinki (Edinburgh, 2000); only after approval for the study has been obtained from the relevant regulatory authority and relevant independent ethics committee (IEC). The institutional review board (IRB)/IEC must review and approve the protocol and informed consent form (ICF) before any subjects are enrolled. The subject must be consented using the approved ICF before any procedures specified in the protocol are performed.

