3 STUDY OBJECTIVES

3.1 Primary Objective

Perform quantitative analysis of the immunologic and genetic changes in immune cell populations in lesional and non-lesional skin after dupilumab treatment (15 AD patients) at weeks 2, 4, 12 compared to baseline week 0. The immunologic and genetic profiles in AD patients will also be compared to healthy control skin surgical discard specimens (n=15). The primary endpoint is the percent change from pre-treatment baseline of CD4+ T effector cells expressing IL-4 at weeks 2, 4, 12 in dupilumab-treated patients.

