5 CRITERIA FOR EVALUATION

5.1 Primary Analysis Endpoint

Percentage change from pre-treatment baseline of CD4+ T effector cells expressing IL-4 at weeks 2, 4, 12 in dupilumab-treated patients.

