14.4 Sample Size

15 subjects will receive dupilumab for a treatment period of 52 weeks (i.e. last injection on week 50). All subjects will undergo skin biopsies for molecular profiling.

Sample size justification

CyTOF: We estimate the minimum effect size that would be clinically relevant would be a reduction in lesional IL-4 positive, CD4+ T lymphocytes of 10%. The standard deviation of the change in lesional IL-4 positive, CD4+ T lymphocytes in the patient population is estimated at 10%. Therefore, our standardized effect size is 1.00. For the statistical analysis, we will set alpha at 0.05, beta at 0.20 (power = 0.8). The resulting sample size estimate for a one sample paired t test is 9 patients. Our proposal uses a total n=15.

RNA-seq: To determine statistical power to identify differentially expressed genes as measured by RNA-seq, we used the Scotty (Busby et al.) power calculator which uses a t-statistic and incorporates the variance attributable to read depth. Performing RNA-seq on 15 samples before and after treatment to a read depth of 50 million per sample as proposed here, we can detect >97% of transcripts displaying 2X fold change and >80% of transcripts displaying 1.5X fold change with p<0.01 (Figure 4).

[figure not shown]

Fig 4. Power to detect differentially expressed genes using RNA-Seq.

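### The primary analysis reads as six paired t-tests with no rule for success, while the stated alpha and power describe one lesional test

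*Combined protocol and SAP*

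**What the plan says.** **Analysis.** Section 14.1 is a single sentence: "One sample paired t-test comparing percentage change in lesional and non-lesional IL-4 positive, CD4+ T effector cells at weeks 2, 4, 12", each compared with baseline.

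**Endpoint.** The places that define it do not agree on scope.
- The synopsis endpoint row names both tissues and all three weeks: "CD4+ T effector cells in lesional and non-lesional skin expressing IL4 at weeks 2, 4, 12 in dupilumab-treated patients".
- The synopsis statistics row names both tissues but no week: "One sample paired t test comparing mean change in lesional and non-lesional IL-4 positive, CD4+ T effector cells compared to baseline".
- Section 3.1 names the weeks but no tissue in its endpoint sentence: "The primary endpoint is the percent change from pre-treatment baseline of CD4+ T effector cells expressing IL-4 at weeks 2, 4, 12". Section 5.1 does the same: "Percentage change from pre-treatment baseline of CD4+ T effector cells expressing IL-4 at weeks 2, 4, 12 in dupilumab-treated patients".

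**Sample size.** Section 14.4 takes as its smallest relevant effect a "reduction in lesional IL-4 positive, CD4+ T lymphocytes of 10" percent, with an SD of change of 10%, hence a standardized effect of 1.00. It sets alpha at 0.05 and power at 0.80, and concludes: "The resulting sample size estimate for a one sample paired t test is 9 patients". The planned number is 15. It names no week and no sidedness, and gives no effect or SD for non-lesional skin.

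**Later SAP.** Section 14 commits to a detailed SAP before the final study data are analysed. It does not mention multiplicity.

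**The concern.** A single alpha of 0.05 has its usual meaning only if one test, or a stated rule for combining tests, decides the primary question. Here several tests are labelled primary and nothing says how they combine. The two simplest rules have opposite consequences. If one significant result among the set is enough, the chance of a false primary finding exceeds the nominal level. If every result must be significant, the error rate is safe, but power is that of a joint requirement and not of the one test that was sized.

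The study is single-arm and mechanistic. What is at stake is how firmly a primary finding can be stated, not a treatment decision.

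**Working it through.** **Inputs from the documents.** Two tissues and three weeks (14.1, synopsis endpoint), so 2 × 3 = 6 tests; at least three on the wording of 3.1 and 5.1. Lesional effect 10%, SD 10%, so d = 10/10 = 1.00; alpha 0.05; power 0.80; stated n = 9; planned n = 15 (14.4).

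**Assumptions.** Sidedness, correlation between tests and the success rule are not given. Two-sided testing, n = 15 and equal correlations of 0, 0.5, 0.7 and 0.9 are used. The three weeks share a baseline, but that does not fix the correlation of percentage changes, so none of these values is claimed as the true one.

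**1. The plan's own figure.** The normal approximation is n = (z_alpha + z_beta)²/d².
- Two-sided: (1.960 + 0.842)² = 7.85, so 8. One-sided: 7.
- Exact power uses the noncentral t with n − 1 degrees of freedom and noncentrality d√n. It needs 10 patients two-sided and 8 one-sided.
- At n = 9, exact power is 74.8% two-sided and 86.2% one-sided.

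The stated 9 lies among these values. The calculation is sound in kind, but it covers one test. At n = 15 that one test has 94.9% power two-sided.

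**2. Any one result counts as success.** For k independent tests the false-positive rate is 1 − (1 − a)^k:
- six tests, either direction: 1 − 0.95⁶ = 26.5%;
- three tests, either direction: 1 − 0.95³ = 14.3%;
- six tests, reductions only (nominal 2.5%): 1 − 0.975⁶ = 14.1%.

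The correlated cases come from simulation of normal changes at n = 15:

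| Correlation | Any of six, either direction | Any of six, reductions only | Any of three lesional weeks, either direction |
|---|---|---|---|
| 0 | 26.5% | 14.1% | 14.3% |
| 0.5 | 21% | 11% | 13% |
| 0.7 | 17% | 8.6% | 11% |
| 0.9 | 11% | 5.6% | 9% |

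**3. All six required.** There is no inflation. Power depends on the non-lesional effect, which must be assumed. With lesional d = 1.00 and independent tests:
- non-lesional 1.00: 0.949⁶ = 73%;
- non-lesional 0.7 (71.3% power per test): 0.949³ × 0.713³ = 31%;
- non-lesional 0.5 (43.8% per test): 0.949³ × 0.438³ = 7%.

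As the correlation rises to 0.9, simulation takes these to about 89%, 61% and 33%.

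**4. Power under a defined rule, lesional d = 1.00, two-sided.**
- One contrast at 0.05: 94.9% with 15 evaluable and 91.1% with 13.
- One contrast at 0.05/3 = 0.0167: 85.8% with 15 and 78.0% with 13.
- All three lesional weeks significant at 0.05, n = 15: 0.949³ = 85.5% if independent, and about 92% at correlation 0.9.

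**The case against.** **The SAP will settle this.** Section 14 does promise a SAP covering all analyses before the final study data are analysed. That is a real commitment and it may close the gap. It does not say that multiplicity will be addressed. Nor does it exclude earlier looks at the CyTOF results: biopsies end at week 12 and follow-up runs to week 52. A reader might infer that the team intends to pick the best tissue and week afterwards. Nothing in the documents says so.

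**Six is a reading, not a statement.** No section gives the number six, and 14.4 sizes lesional skin only. That is fair. On the narrowest reading three weekly tests remain, with a rate of about 9% to 14% if any one suffices.

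**The study is small and mechanistic.** Also fair, and it limits the consequence. But the protocol itself sets an alpha and a power for its primary endpoint, so those figures should match the analysis.

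**Power is ample.** Partly so. With 15 patients against a calculated 9, even a contrast tested at 0.05/3 keeps 86% power. A reader might infer that the trial is underpowered or that the arithmetic in 14.4 is wrong; neither follows. The margin holds for lesional skin at effect 1.00. For non-lesional skin there is no stated effect or SD to judge it by.

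**Conclusion.** The point holds. Section 14.1 and the synopsis plan six primary tests on the natural reading, and at least three on the wording of 3.1 and 5.1. The alpha and power in 14.4 belong to a single lesional test at an unnamed week.

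The size depends on a success rule that the documents do not give. If any one two-sided result suffices, the error rate is about 11% to 26% for six tests and 9% to 14% for three lesional weeks, over assumed correlations from 0.9 down to 0. If only reductions count, the six-test rate is about 6% to 14% against a nominal 2.5%. If all six are required, there is no inflation and power is unknown: 73% to 89% with a non-lesional effect of 1.00, about 31% to 61% at 0.7, and about 7% to 33% at 0.5.

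It would be too strong to say that the trial's false-positive rate is 26%. That figure needs both independence and an any-one-counts rule, and neither is in the plan.

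**What to change.** Before any CyTOF results are seen, name one primary contrast, in the same words, in the synopsis, 3.1, 5.1 and 14.1: lesional skin (the tissue sized in 14.4) at one week chosen by the sponsor, tested at two-sided 0.05. Then test the other two lesional weeks and the three non-lesional weeks in a stated fixed order, each at 0.05, stopping at the first non-significant result.

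Alternatively, apply Holm across the three lesional weeks. Non-lesional skin is then tested only if all three are significant, or reported as secondary.

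Either way, report estimates with 95% intervals for all six comparisons.

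In 14.4, state the sidedness and the power of the test actually used at effect 1.00: 95% with 15 evaluable and 91% with 13 for one two-sided test, or 86% and 78% for one contrast at 0.05/3. The latter is a conservative figure for Holm. If testing is two-sided, note that 9 patients gives 75% power and that 80% needs 10.

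The cost is wording; no patients, biopsies or visits are added. With a fixed order, later contrasts can be claimed only if earlier ones succeed. All three lesional weeks succeed with about 86% to 92% probability at effect 1.00 and n = 15. The chance of claiming all six depends on the unstated non-lesional effect. Holm avoids ranking the weeks, at the price of a somewhat stricter first test.
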